2.2. Study Objectives and Endpoints

The below objectives and endpoints will be assessed when subjects with a severe eosinophilic asthma phenotype who are not optimally controlled on omalizumab are directly switched from omalizumab to mepolizumab:

Objectives	Endpoints
Primary Objectives	Primary Endpoints

 To describe in a pragmatic situation/setting whether there is an improvement in asthma control from the beginning to the end of the study 	
 Mean change from baseline in Asthma Control Questionnaire-5 (ACQ-5) score at Week 32
Secondary Objectives	Secondary Endpoints

 To determine whether there is an improvement in Health related Quality of Life (HR-QoL) To determine the frequency of asthma exacerbations To evaluate the pharmacodynamic effects 	
 Mean change from baseline in St. George's Respiratory Questionnaire (SGRQ) score at Week 32 Frequency of clinically significant asthma exacerbations over 32 week treatment Ratio to baseline in blood eosinophils at Week 32
Other Objectives	Other Endpoints

 To determine the response to asthma clinical parameters 	
 Percentage of subjects achieving a 0.5-point or greater reduction from baseline in ACQ-5 score at Week 32 Percentage of subjects achieving a 4-point or greater reduction from baseline in SGRQ score at Week 32 Mean change from baseline in pre- and post bronchodilator FEV1 at Week 32 Frequency of exacerbations requiring ED visit/hospitalization during the treatment period Subject/Clinician rated response to therapy Mean change from baseline in treatment satisfaction questionnaire
Exploratory Objectives	Exploratory Endpoints

 To determine the effect on inflammatory biomarkers To characterize patient treatment benefit of mepolizumab 	
 Change from baseline in some inflammatory biomarkers expression at week 32 Subject Exit Interviews
Safety Objectives	Safety Endpoints

 To determine the safety, immunogenicity and tolerability of mepolizumab 	
 Incidence and frequency of Adverse/Serious Adverse Events (including systemic and injection site reactions) Clinically significant change in electrocardiogram (ECGs) Clinically significant change in vital signs

Objectives	Endpoints
	
• Incidence of immunogenicity

2.3. Study Design

Overview of Study Design and Key Features											
omalizumab		switch to mepolizumab 100 mg SC every 4 weeks									
C-2 weeks 1-4 weeks											
											
Design Features	
 An open label, single arm, 32-week treatment, multi-center study in subjects with severe eosinophilic asthma not optimally controlled with current omalizumab treatment who are switched from omalizumab to mepolizumab 100mg administered subcutaneously (SC) every 4 weeks. Patients with severe eosinophilic asthma who are receiving omalizumab, but are not optimally controlled will be eligible to participate and will be identified through the ACQ-5 with a screening (Visit 1) and baseline (Visit 2) score of ≥ 1.5 and a history of ≥ 2 exacerbations in the past 12 months. 										
	
 Subjects will remain on their current maintenance therapy throughout the run-in period, including Omalizumab. At Visit 2 subjects will discontinue their Omalizumab treatment and be switched to open-label mepolizumab (100 mg SC) every 4 weeks for 32 weeks (there is no wash-out period between the therapies). If patients require any additional maintenance therapy (except for omalizumab), they will remain receiving it throughout the treatment period. 										
Treatment Assignment	
 At week 0 (Visit 2) approximately 120 eligible subjects who meet the continuation to treatment criteria will receive open-label mepolizumab 100 mg SC into the upper arm or thigh every 4 weeks with the last dose being given at week 28 (Visit 9). A web based interactive system RAMOS NG will be used to dispense mepolizumab from Visit 2 to Visit 9. 										
	
 No interim analysis of data is planned for this study. A complete analysis in accordance with all study objectives and endpoints will be performed after all subjects have completed the study. Decisions regarding the analyses, specified in this RAP document, will be made prior to Database Freeze of the study data. 										

2.4. Statistical Hypotheses

This study is designed to investigate whether subjects not optimally controlled on omalizumab can be effectively and safely switched to treatment with mepolizumab to improve asthma control. As there is no control arm in this study, comparisons in ACQ-5 score will be made to baseline. The first hypothesis to be tested will be for superiority of mepolizumab 100 mg SC treatment vs. baseline.

The potential of a ‘placebo effect’ within the mepolizumab treated subjects has been considered. In the protocol this was estimated as an improvement of -0.55 (SE: 0.05) from baseline in ACQ-5 score, based on the placebo effect observed in mepolizumab subjects from Phase 3 severe asthma studies (meta-analysis of double-blind studies MEA112997 and MEA115588). Improvements from baseline in ACQ-5 score will be assessed against this historical ‘placebo effect’. For further information regarding this historical ‘placebo effect’ please refer to Section 7.1.3.

Significance tests will be performed at the two-sided 5% alpha level (one-sided 2.5%).

3. PLANNED ANALYSES

3.1. Interim Analyses

No interim analysis of data is planned for this study.

3.2. Final Analyses

The final planned primary analyses will be performed after the completion of the following sequential steps:

1. All subjects have completed the study as defined in the protocol
2. All required database cleaning activities have been completed and final database release and database freeze has been declared by Data Management.

4. ANALYSIS POPULATIONS

Population	Definition / Criteria	Analyses Evaluated
All Subjects Enrolled (ASE) Population	
 Comprised of all subjects enrolled and for whom a record exists on the study database. 	
 Screen and run-in failures
Intent-to-Treat (ITT) Population	
 Comprised of all subjects who receive at least one dose of mepolizumab. 	
 Study Population Efficacy Safety
Per Protocol (PP) Population	
 Comprised of all subjects in the ITT population who have not been identified as full protocol deviators with respect to criteria that are considered to impact the primary efficacy analysis. 
The decision to exclude a subject from the PP Population or exclude part of their data from the PP Population analyses will be made prior to freezing the study database.
 
Protocol deviations that would exclude subjects from the PP population are defined in Section 4.1 (Protocol Deviations) and (Appendix 1: Protocol Deviation Management and Definitions for Per Protocol Population).
	
 Supplementary analysis of the primary endpoint

NOTES :

- Please refer to [Appendix 13: List of Data Displays](#) which details the population to be used for each displays being generated.

4.1. Protocol Deviations

- All protocol deviations will be tracked by the study team throughout the conduct of the study in accordance with the Protocol Deviation Management Plan.
 - Data will be reviewed prior to freezing the database to ensure all important deviations and deviations which may lead to exclusion from the Per Protocol analysis are captured and categorised on the protocol deviations dataset.
 - This dataset will be the basis for the summaries and listings of protocol deviations.
- Important protocol deviations (including deviations related to study inclusion/exclusion criteria, conduct of the trial, patient management or patient assessment) will be summarised and listed.
- Important deviations which result in exclusion from the Per Protocol population will also be summarised and listed. (Please refer to [Appendix 1: Protocol Deviation Management and Definitions for Per Protocol Population](#)).
- A separate summary and listing of all inclusion/exclusion criteria deviations will also be provided. This summary will be based on data as recorded on the inclusion/exclusion page of the eCRF.

5. CONSIDERATIONS FOR DATA ANALYSES AND DATA HANDLING CONVENTIONS

Table 2 provides an overview of appendices within the RAP for outlining general considerations for data analyses and data handling conventions.

Table 2 Overview of Appendices

Section	Component
10.1	Appendix 1: Protocol Deviation Management and Definitions for Per Protocol Population
10.2	Appendix 2: Time & Events
10.3	Appendix 3: Assessment Windows & Visit Slotting
10.4	Appendix 4: Treatment Phases
10.5	Appendix 5: Data Display Standards & Handling Conventions
10.6	Appendix 6: Derived and Transformed Data
10.7	Appendix 7: Premature Withdrawals & Handling of Missing Data
10.8	Appendix 8: Values of Potential Clinical Importance
10.9	Appendix 9: Multicenter Studies
10.10	Appendix 10: Examination of Covariates and Subgroups
10.11	Appendix 11: Model Checking and Diagnostics for Statistical Analyses
Other RAP Appendices	
10.12	Appendix 12: Abbreviations & Trade Marks
10.13	Appendix 13: List of Data Displays
10.14	Appendix 14: Example Mock Shells for Data Displays

6. STUDY POPULATION ANALYSES

6.1. Overview of Planned Analyses

The study population analyses will be based on the Intent-To-Treat (ITT) population, unless otherwise specified.

[Table 3](#) provides an overview of the planned study population analyses, with full details of data displays being presented in [Appendix 13: List of Data Displays](#).

Table 3 Overview of Planned Study Population Analyses

Endpoint / Parameter / Display Type	Data Displays Generated		
	Table	Figure	Listing
Subject Disposition			
Analysis Populations	Y		
Reasons for Screen and Run-in Failure	Y		Y
Failed Inclusion/Exclusion/Continuation criteria	Y		Y
Subjects by Region, Country and Site	Y		
Reasons for Subject Withdrawal From Study	Y		Y
Reasons for Subject Withdrawal From Investigational Product	Y		Y
Time to Withdrawal From Investigational Product		Y ^[1]	
Demographic and Baseline Characteristics			
Demographic Characteristics	Y		Y
Age Ranges	Y		
Race and Racial Combinations	Y		Y ^[2]
Race and Racial Combination Details	Y		
Demographic and Baseline Disease Characteristics			
Asthma History and Baseline Disease Characteristics	Y		
Previous Exacerbation History	Y		
History of Tobacco Use	Y		
Baseline Lung Function Results	Y		
Past and Current Medical Conditions	Y		
Cardiovascular Assessments (Family History/Screen Questions)	Y		
Prior and Concomitant Medications			
History Xolair Use (including regime, duration of treatment)	Y		
Asthma Concomitant Medications by Respiratory Medication Class	Y		
Non-Asthma Concomitant Medications Taken During Treatment	Y		
Relationship between ATC level 1, Ingredient and verbatim text			Y

Endpoint / Parameter / Display Type	Data Displays Generated		
	Table	Figure	Listing
Protocol Deviations			
Important Protocol Deviations	Y		Y
Protocol Deviations Resulting in Exclusion from PP Population			Y

NOTES : Y = Yes display generated. [1] Kaplan Meier plot; [2] Listing of race as collected in eCRF.

7. PRIMARY STATISTICAL ANALYSES

7.1. Efficacy Analyses

7.1.1. Overview of Planned Efficacy Analyses

The primary efficacy analyses will be based on the Intent-To-Treat (ITT) population. Additional sensitivity analysis will be performed on the Per Protocol population.

Table 4 provides an overview of the planned efficacy analyses, with full details of data displays being presented in [Appendix 13: List of Data Displays](#).

Table 4 Overview of Planned Efficacy Analyses

Endpoint	Absolute ^[1]								Change from Baseline ^[1]							
	Stats Analysis			Summary		Individual			Stats Analysis			Summary		Individual		
	T	F	L	T	F	F	L	T	F	L	T	F	F	L	T	F
Primary Endpoint																
Asthma Control Questionnaire (ACQ-5)																
On-treatment & Off-treatment ^{[2] [3]}	Y ^[4]				Y				Y ^[4]	Y ^[5]		Y	Y		Y	

NOTES :

- T = Table, F = Figure, L = Listing, Y = Yes display generated.
- Stats Analysis = Represents TFL related to any formal statistical analyses (i.e. modelling) conducted.
- Summary = Represents TFL related to any summaries (i.e. descriptive statistics) of the observed raw data.
- Individual = Represents FL related to any displays of individual subject observed raw data.

1. Absolute and change from baseline summaries combined into a single display.
2. To be generated for Intent-To-Treat (ITT) population and Per-Protocol (PP) population.
3. Subgroup analyses to be repeated for Intent-To-Treat (ITT) population and all subgroups listed within Section [10.10.2](#).
4. Table to include both Least Square Means and Least Square Mean Changes and estimated treatment difference (Mepolizumab-Historical Placebo) and 95% confidence interval at each visit from Mixed Model Repeated Measures (MMRM) Analysis.
5. Figure to present Least Square Mean Changes and corresponding 95% confidence intervals at each visit from MMRM Analysis

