### 9.2. Sample Size Considerations

#### 9.2.1. Sample Size Assumptions

The primary analysis will utilise within-subject changes from baseline. As this study is uncontrolled, the potential of a 'placebo effect' within the mepolizumab treated subjects will be considered. A meta-analysis of two previous severe asthma studies with mepolizumab (MEA115588 and MEA112997) estimated a change from baseline at Week 32 of -0.55 and -0.88 in the placebo and mepolizumab groups respectively, with mepolizumab presenting a benefit of -0.34 over placebo.

The following sample size estimates are based on a residual standard deviation of 0.96 units and are based upon the aforementioned meta-analysis. These estimates assume that 15% of subjects will prematurely withdraw from the study and therefore have missing

data at Week 32. This primary analysis will use the “missing at random” assumption for missing data.

With a sample size of 120 treated subjects, it is estimated that this study has over 90% power to detect a statistically significant improvement from baseline. Further it is estimated that a significant improvement over the ‘placebo effect’ of -0.55 from baseline in ACQ score will be observed at the two-sided 5% level of significance if the observed change from baseline is at least -0.74 units.

If the true change from baseline is -0.86 units, then the study has a probability of 90% of observing a change from baseline of at least -0.74 units and therefore the study has 90% power for declaring statistical significance over the ‘placebo effect’.

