7.1.3. Analysis Comparing Against A Historical Placebo Effect

We will perform two separate analyses of the primary endpoint comparing to a historical 'placebo effect'.

[figure not shown]
Firstly, as specified in the protocol, a meta-analysis of previous exacerbation double-blind studies, MEA112997 and MEA115588, gave an estimate of -0.55 (SE: 0.05), for the improvement in the ACQ-5 score for placebo subjects at Week 32 compared to baseline. The observed improvement in this study for following mepolizumab treatment will be compared to this historical improvement on placebo.

Secondly, a meta-analysis has been performed of subjects within studies MEA115588 and 200862 who reported previous Xolair use, which may represent a more comparable population for this study. Study 200862 has completed since the protocol was finalised and previous Xolair usage was not collected in study MEA112997.

At Week 32 an estimate of -0.29 (SE: 0.248) was reported in the MEA115588 study while at Week 24 study 200862 reported an estimate of -0.03 (SE: 0.164) for the improvement in the ACQ-5 score for placebo subjects who previously used Xolair.

Weighted meta-analysis was performed on these values to get the combined estimate of -0.11 (SE: 0.14) for the historical placebo effect (Figure 1). This shows a reduction in the ACQ-5 score, but not as large as that specified in the protocol. The observed improvement in this study for mepolizumab vs. baseline will be also compared to this historical improvement on placebo.

Figure 1 Meta-analysis of ACQ-5 Placebo Effect in Previous Xolair Users

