10.10.2. Handling of Subgroups

The following subgroups are of interest within this study. A separate exploratory analysis of the primary endpoint within each subgroup will be carried out.

Subgroup categories may be further collapsed if there are a small number of subjects in a treatment arm within a subgroup leading to model convergence issues.

The following subgroups are of interest for the primary efficacy endpoint:

- Exacerbations in previous year: ≤ 2 , 3, 4+ exacerbations
- Baseline blood eosinophils: < 150 , $\geq 150 - < 300$, $\geq 300 - < 500$, ≥ 500 cells/ μ l

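### Read literally, SAP Table 4 extends the historical-placebo difference to every subgroup and visit, but the SAP has only overall benchmarks meant for Week 32

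*SAP*

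**What the plan says.** Table 4 in SAP 7.1.1 has one row for the primary endpoint, ACQ-5, and its notes set the content.

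- Note 3 is attached to the row: "Subgroup analyses to be repeated for Intent-To-Treat (ITT) population and all subgroups listed within Section" 10.10.2.
- Note 4 is attached to the statistical-analysis table cells of the same row. It requires least-squares means, their changes from baseline and the "estimated treatment difference (Mepolizumab-Historical Placebo) and 95% confidence interval at each visit".

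SAP 10.10.2 names two subgroup factors, prior exacerbations (three strata) and baseline blood eosinophils (four strata), and says "A separate exploratory analysis of the primary endpoint within each subgroup will be carried out". It specifies no output of its own.

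SAP 7.1.2 lists the historical-placebo difference among the model results for the primary endpoint and again among the supportive analyses, both times at Week 32. Subgroup analyses are a separate item.

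SAP 7.1.3 provides two benchmarks. The first is "an estimate of -0.55 (SE: 0.05), for the improvement in the ACQ-5 score for placebo subjects at Week 32". The second, for placebo subjects with previous Xolair use, is -0.11 (SE 0.14). It pools a Week 32 estimate from one study with a Week 24 estimate from another. Neither is split by prior exacerbations or eosinophils.

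**The concern.** In a single-arm study, the historical benchmark is the only thing that turns a change from baseline into something labelled a treatment difference. The label is fair only if the benchmark describes what comparable patients on placebo would have done at that time point. Followed to the letter, notes 3 and 4 would print a control-adjusted estimate and interval for each stratum and visit, using a number estimated for neither.

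Prior exacerbation count and eosinophil level are also factors that readers may use to decide which patients to switch. An interval excluding zero in one stratum is easily read as a drug effect in those patients, when it may reflect a placebo change there that differs from the overall value.

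**Working it through.** **Inputs.** From Protocol 9.2.1: "The following sample size estimates are based on a residual standard deviation of 0.96 units"; 120 treated subjects; and "These estimates assume that 15% of subjects will prematurely withdraw from the study", so 120 x 0.85 = 102 with Week 32 data. From SAP 2.4: two-sided 5%, one-sided 2.5%. From SAP 7.1.3: the two benchmarks and their SEs.

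**Step 1: reproduce the plan's figures.** With -0.55 treated as a fixed constant:

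- SE = 0.96/sqrt(102) = 0.0951.
- Threshold = -0.55 - 1.96 x 0.0951 = -0.736 (normal) or -0.739 (t). The protocol states -0.74.
- Power at a true change of -0.86 = Phi(0.31/0.0951 - 1.96) = 90.3% (normal) or 89.8% (t). The protocol states 90%.
- Second benchmark, inverse-variance pooling: weights 1/0.248^2 = 16.26 and 1/0.164^2 = 37.18. Estimate = (16.26 x -0.29 + 37.18 x -0.03)/53.44 = -0.109; SE = 1/sqrt(53.44) = 0.137. The SAP states -0.11 (0.14).

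The overall Week 32 figures are therefore consistent with the documents' inputs.

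**Step 2: what a stratum difference would estimate.** Let p be the change the stratum would show on placebo, d the drug effect in it, and c the benchmark.

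- Change from baseline = p + d.
- Displayed difference = p + d - c = d + (p - c).
- Bias = p - c, which is zero only if the stratum's placebo change equals the overall benchmark. The documents give no p for any stratum.
- Between two strata, c cancels, so the contrast is the same as for change from baseline.

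The same algebra applies to a visit other than Week 32. No benchmark is given for other visits, apart from the Week 24 component of the second one.

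**Step 3: illustration.** Assumptions that are not in the documents: completers split equally over the strata (102/4 = 25.5 or 102/3 = 34), no drug effect, and a stratum placebo improvement larger than the benchmark by x.

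SE = sqrt(0.96^2/m + SE_benchmark^2), and the chance that the 95% CI shows benefit = Phi(x/SE - 1.96).

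| Benchmark | m | SE | x = 0 | x = 0.1 | x = 0.2 | x = 0.3 |
|---|---|---|---|---|---|---|
| -0.55 (SE 0.05) | 25.5 | 0.197 | 2.5% | 7.3% | 17.3% | 33.2% |
| -0.55 (SE 0.05) | 34 | 0.172 | 2.5% | 8.4% | 21.3% | 41.4% |
| -0.11 (SE 0.14) | 25.5 | 0.236 | 2.5% | 6.2% | 13.3% | 24.5% |

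Treating -0.55 as fixed gives 7.6%, 18.2% and 35.1% at m = 25.5. If the stratum's placebo improvement is smaller than 0.55, the error runs the other way: at m = 25.5 the chance falls to 0.7% for a shortfall of 0.1 and 0.1% for 0.2, and a real benefit could be hidden.

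**The case against.** The strongest reply is that the problem arises only from combining two footnotes in an overview table. Section 7.1.2 lists the historical comparison and the subgroup analyses as separate items, 7.1.3 describes two comparisons of the primary endpoint without mentioning subgroups, and 10.10.2 calls the subgroup work exploratory. Appendix 13, to which Table 4 refers for detail, titles Tables 2.4 and 2.5 as change from baseline by subgroup. It lists no subgroup version of the model figure that the same Table 4 row requires, so note 3 does not carry every cell into the subgroups.

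Much of this stands. A reader might infer that each stratum will be tested against the wrong control. The documents do not support that: no section orders a subgroup test against a benchmark, note 4 asks for a difference and interval, and without stratum placebo data nobody can say that the overall value is wrong for a stratum, or in which direction. A reader might also count seven strata by eight post-baseline visits, or 56 differences per benchmark. That count depends on note 4's each-visit wording, which 7.1.2 contradicts.

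Appendix 13 does not settle the matter, however. Table 2.2, the overall model table to which note 4 plainly applies, does not name historical placebo in its title either. The Per Protocol model table that note 2 calls for is not in the list at all (Table 2.3 is a responder analysis). Silence there is not exclusion, and the shells are in separate documents.

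It is also fair to say that removing a constant leaves the ranking of strata unchanged, so prognosis and drug effect can be confused in the change-from-baseline tables too. That limit comes from the single-arm design. What the restriction removes is the label and interval that suggest a control adjustment has been made.

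**Conclusion.** The point holds as a drafting defect with a minor consequence. Notes 3 and 4, taken as written, call for historical-placebo differences in strata and at visits for which the SAP has no benchmark, and note 4 conflicts with 7.1.2 over which visits are meant. Any such number would be a change from baseline under a label it cannot support.

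The size and direction of the bias cannot be determined from the documents. The range of roughly 7% to 33% against 2.5% rests on an assumed shift of 0.1 to 0.3 in one direction, about 25 completers, SD 0.96 and the -0.55 benchmark with its SE. It describes how an exploratory display could mislead, not an error rate of a planned test. The overall ITT and PP comparisons at Week 32 are not affected.

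**What to change.** Amend note 4 so that the historical-placebo difference and its 95% CI are shown only for the overall ITT and PP populations at Week 32. This also resolves the conflict with 7.1.2. In Tables 2.4 and 2.5, show only the least-squares mean change from baseline with its 95% CI, and state there and in 10.10.2 that without a concurrent control these results cannot separate prognosis from drug effect.

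The cost is about one sentence in each place. The exploratory subgroup tables would have no placebo-referenced column. If one is wanted, it needs placebo estimates for the same strata from the sponsor's placebo-controlled studies, with their standard errors carried into the interval, which would then be wider.
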